# 6.5. Concomitant Therapy

Any medications taken and changes in medications from the time the participant signing the study specific informed consent, up to final study contact Day 28 (±3 days) will be recorded in the source data. Any medication (including over-the-counter or prescription medicines, vitamins, and/or herbal supplements) or other specific categories of interest) that the participant is receiving at the time of enrolment or receives during the quarantine/outpatient stage will be stored, prescribed and administered in line with their label-specific requirements, and recorded according to the parameters required by the clinical database.:

Participants will be reminded to refrain from using any over-the-counter medication without the approval of the Investigator and must notify the site as soon as possible if they are prescribed any medication. All medications must be stopped prior to the planned date of dosing with IMP/viral challenge (whichever occurs first) unless in the opinion of the Investigator and/or Sponsor's Medical Expert (SME), the medication will not interfere with the study procedures or compromise participant safety.

Medications prohibited throughout the study are shown in Table 3.

**Table 3 - Prohibited Medications** 

Prohibited medication	Washout		
Systemic (oral and parenteral) antiviral drugs.	4 weeks prior to first study visit.		
Use or anticipated use during conduct of the study of concomitant medications (prescription and non-prescription), including vitamins or herbal and dietary supplements within the specified windows, unless in the opinion of the Investigator the medication will not interfere with the study procedures or compromise participant safety.	7 days prior to the planned date of viral challenge:  •Herbal supplements  •Any medication or product (prescription or over the counter) for symptoms of nasal congestion  •Short and long-acting antihistamines.  Within 21 days prior to the planned date of viral challenge:  •Chronically used medications, vitamins or dietary		

Prohibited medication	Washout		
	be moderate/potent inducers or inhibitors of CYP450 enzyme.		

Any concomitant medication required for the participant's welfare may be given by the Investigator. However, it is the responsibility of the Investigator to ensure that details regarding the medication and the reason for its use are recorded appropriately in the source notes to permit their transfer to the clinical database.

The use of paracetamol and/or other allowed medications is permissible within 7 days before the date of first dosing with IMP/viral challenge (whichever occurs first) at PI discretion. During the study periods, the Investigator may permit a limited amount of paracetamol (no more than 4 g per day i.e. maximum daily dose) or topical medication, as clinically required for the treatment of headache or any other pain. Other medication to treat AEs may be prescribed if required.

Medications which are permitted throughout the study are shown in Table 4 below:

Table 4 - Permitted Medication

Permitted medication	Time period		
Paracetamol	Maximum 4g daily throughout the study duration at PI discretion.		
Oral contraceptives Allowed at any time during the study.			
Prescription and non-prescription medications, including vitamins or herbal and dietary supplements, not listed in prohibited medications are subject to approval by the PI.			

#### 6.6. Dose Modification

Modification to the Palivizumab dose from 8mg/kg to 15mg/kg may be required for Part 2 of the study. Dose selection for Part 2 will be made by the Sponsor based on a review of the PK data obtained from at least 6 participants dosed with 8mg/kg of Palivizumab in Part 1; and a confirmation of no safety or tolerability concerns from the Safety Data Review Meeting as described in Section 10.1.5.

The PK assessment up to and including Day 12 exposure will be used as a decision information for the dose for Part 2. PK exposure data from at least 5 out of 6 participants is required for dose decision making with a projected exposure of  $\geq$ 40 µg/mL on Day 12.

# 7. Discontinuation of Study Intervention/Withdrawal

# 7.1. Participant Withdrawal

A participant may withdraw their consent to participate in the study at any time, for any reason, without prejudice to his/her future medical care. Participants may decline to give a reason for their withdrawal. Additionally, the PI may withdraw a participant if, in their clinical judgement, it is in the best interest of the participant or if the participant cannot comply with the protocol. Wherever possible, the tests and evaluations listed for the Early Withdrawal Visit (EWV) should be carried out, and if clinically indicated, the participant should be invited back for a final follow up visit. If a participant withdraws from the study during the quarantine phase, an EWV will be completed on the day where possible prior to the participant leaving the unit. It is likely that some of the assessments required as part of the EWV will already have been performed for the study day as per SOA, in this case the completed assessments will not be repeated on the same day unless clinically indicated.

The sponsor should be notified of all study withdrawals in a timely manner, and in cases where the withdrawal is due to a medical reason the participant would be referred to his/her GP.

Participants will be counselled that early withdrawal from the viral challenge phase of the study is strongly discouraged, as it may pose a risk both to the participant and his/her contacts. In the event of a participant insisting on early withdrawal during the challenge isolation period, the participant will be encouraged to stay and would be advised of the potential risks of carrying RSV infection into the community, and to vulnerable groups in particular as described in Section 2.3.1

If the participant withdraws consent for disclosure of future information, the Sponsor may retain and continue to use any data collected before such a withdrawal of consent.

If a participant withdraws from the study, he/she may request destruction of any samples taken and not tested, and the Investigator must document this in the site study records.

## 7.2. Participant Discontinuation

Participants will be withdrawn from study intervention for the reasons listed below. These participants must not receive any additional intervention but should continue to be followed for safety. Additional unscheduled visits may be performed for safety reasons.

- Non-compliance with the study requirements and restrictions.
- Clinically significant abnormal laboratory findings, which in the opinion of the Investigator(s) and/or Sponsor, precludes further participation in the study.
- Development of inter-current illness which, in the opinion of the Investigator would compromise the health of the participant or the study objectives.
- The Investigator's decision that withdrawal from further participation would be in the participant's best interest.
- Termination of the study at the discretion of the Investigator(s) or Sponsor for safety, behavioural, or administrative reasons.
- The wish of the participant.

- Any intervention related SAEs.
- Anaphylactic reaction following dosing.
- The participant becomes pregnant (if pregnancy is specified as an exclusion criterion).

Participants who are withdrawn from the study, will be requested to attend an Early Withdrawal Visit, with assessments as detailed in the SoA.

#### 7.2.1. Temporary Discontinuation/Temporary Delay in Enrolment

At the first study visit, if a participant is found to be ineligible due to transient circumstances (such as acute disease and/or fever), dosing with Palivizumab will be postponed until transient circumstances have been resolved and the participant will be re-invited to a later quarantine group within the allowed time window. For participant rescreening refer to Section 5.4

#### 7.3. Lost to Follow up

A participant will be considered lost to follow-up if he or she repeatedly fails to return for scheduled visits and is unable to be contacted by the study site.

The following actions must be taken if a participant fails to return to the clinic for a required study visit:

- The site must attempt to contact the participant and reschedule the missed visit as soon as
  possible and counsel the participant on the importance of maintaining the assigned visit schedule
  and ascertain whether or not the participant wishes to and/or should continue in the study.
- Before a participant is deemed lost to follow up, the investigator or designee must make every effort to regain contact with the participant (where possible, 3 telephone calls and, if necessary, a follow-up letter to the participant's last known mailing address or local equivalent methods). These contact attempts should be documented in the participant's medical record.
- Should the participant continue to be unreachable, he/she will be considered to have withdrawn from the study.

## 7.4. Participant Replacement Strategy

Participants who withdraw or are discontinued from the study may be replaced in order to achieve the planned evaluable number of participants as follows, if deemed appropriate by the PI and with the approval of the Sponsor:

- In Part 1, withdrawals or early discontinuation prior to the completion of all scheduled clinic visits up to and including Day 12 Visit may be replaced.
- In Part 2, participants who have been dosed but not inoculated may be replaced. The replacement participant will be assigned to the same group as the original (discontinued) participant.

  Participants who have been dosed and inoculated but did not complete the study may be replaced.

# 7.5. Stopping Rules

The PI and the SME will perform safety reviews on available clinical and virology data as appropriate during the quarantine period.

Three clinical scenarios relating to the incidence of SAEs/SUSAR during the study and the procedures that should be performed in each case are presented in Table 5.

Table 5 - Study Stopping Rules

Status	Criterion	Procedure		
1	A report has been received of one (or more) SUSAR in anyone (or more) participant(s).	If such a status occurs at any point during the study, then further administration of Palivizumab will not take place. The PI and the SME will review the data and make decisions on whether it is appropriate to recommence dosing (via a substantial amendment, if indicated) or terminate the study.		
2	No SUSAR have been reported but an overall pattern of clinical changes or symptoms exists, attributed to the IMP, which may appear minor or moderate in terms of individual AEs, but which collectively represent a concern for safety.	If such a status occurs at any point during the study, then further administration of IMP will not take place. The PI and the SME will review the data and make a decision on whether it is appropriate to recommence dosing (via a substantial amendment, if indicated) or terminate the study.		
3	Unexpected virus-related SAE or Unexpected virus-related AEs of clinical concern have been reported following Human Viral Challenge. *Expectedness will be assessed by referring to the challenge virus dossier	If such a status occurs at any point during the study, then the PI and the SME will review the data and make a decision based on expectedness* of the viral event.  If the event is unexpected, further administration of the virus will not take place. The PI and the SME will review the data and make a decision on whether it is appropriate to recommence inoculation (via a substantial amendment, if indicated) or terminate the study.		

In any event, participant follow-up should continue until resolution or stabilisation of AEs and final follow-up on Day 28 (± 3 days).

# 8. Study Assessments and Procedures

Study procedures and their timing are summarised in the SoA. Protocol waivers or exemptions are not allowed. Adherence to the study design requirements, including those specified in the SoA, is essential and required for study conduct. Immediate safety concerns should be discussed with the Sponsor upon occurrence or awareness to determine if the participant should continue or discontinue study intervention

All screening evaluations must be completed and reviewed to confirm that potential participants meet all eligibility criteria. The investigator will maintain a screening log to record details of all participants screened and to document eligibility or record the reasons for screening failure, as applicable.

For all study assessments, the value obtained nearest to dosing will be used as the baseline measure for assessments, unless stated otherwise.

Procedures conducted as part of the hVIVO Generic Screening process and obtained before signing of the study specific Informed Consent Form (ICF) may be utilised for screening or baseline purposes provided the procedures met the protocol-specified criteria and were performed within the time frame defined in the SoA.

Where applicable, unless otherwise stated, normal ranges will be identified in the Investigator Trial Master File (TMF).

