### MB05-P-01-20 Protocol Final V2.0

+	Only the applicable Inclusion/Exclusion criteria will be reviewed at each time point.
*	All screening assessments will be performed under hVIVO Generic Screening process. Results of tests or examinations performed under hVIVO Generic Screening process, and within 90 days (90 days for viral serology and 56 days for other assessments including safety laboratory test) prior to quarantine admission may be used to determine eligibility without the need to repeat the assessment following study specific consent.
а	Height will be taken at Screening only.
b	Vital signs will be taken at the same time each day (± 1 hour).
С	Distribution of paper issues and bags will start on Day -2, with the first collection on Day -1. Thereafter collection of tissues will occur at the same timepoints (± 1 hour) with tissues distributed 24 h ahead.
d	Assessments will be performed at the same time each day during quarantine (± 1 hour). Where respiratory assessments timepoints occur together, the order of assessments will typically be 1) FOT followed by 2) PEF followed by 3) Spirometry.
е	A serum follicle stimulating hormone (FSH) test will be performed in all post-menopausal women
f	Blood serum pregnancy test (ß-HCG) will be performed in all female participants
g	Blood will be drawn under non-fasted conditions. Repeat bloods may be drawn under fasted conditions if a lipid profile (triglyceride) or glucose is required (at PI discretion).
h	Virus serology (RSV neutralisation antibody assay) will be performed to determine eligibility and seroconversion. Exploratory RSV-induced immune responses may also be assessed.
i	Nasopharyngeal swab or nasal wash for respiratory virus screen to assess for the presence of other respiratory viruses; if found positive the participant will not be eligible for the current quarantine.
j	PK blood samples are taken before the start of infusion; at end of infusion, 15mins, and 0.5, 1, 4, 8, and 12 h after infusion; and at 1, 2, 3, 7, 13, 21 and 29 days after infusion. Allowable time windows are described I section 8.19.3.
k	Post inoculation Nasal virology samples will be collected at the same time each day during quarantine (± 1 hour) and used for qRT-PCR and viral culture assay.  Optional exploratory RSV-induced immune responses may also be assessed. Nasal wash is optional under PI discretion, if NPS are being collected BD and used for viral load assessments.
I	Can be performed on Study Day -3 or Study Day -2.

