#### 4.1.4. Part 2 duration

The total duration of study participation for a participant is up to approximately 122 days, with the following sequence and duration of study periods:

- **Screening** phase: from Day -90 to Day -4 pre-quarantine admission (Historical generic screening data collected through the hVIVO Generic Screening process may be transferred to this study after the study-specific consent form has been signed by the participant).
- **Inpatient phase:** Participants will be resident in the Quarantine Unit for approximately 16 days (from Day -3 to Day +12). Procedures will include:
  - o Pre-HVC:
- Admission to Quarantine Unit on Day -3
- Study intervention I.V. dosing on Day -1
- o HVC:
- Challenge Virus inoculation on Day 0 (window 1 to 2 days post-treatment)
- Post-HVC
- Day 0 onwards and each day study assessments will be conducted as per Schedule of Activities
- Participants will be discharged from the Quarantine Unit on Day12 (or may remain longer at the Principal Investigator's discretion)
- Outpatient phase: study assessments will be conducted
  - Clinic visit for PK sample on Day 20 (±2 days)
  - Final safety follow-up visit(s): Day 28 (±3 days)

The study will be conducted by hVIVO which has extensive experience with RSV challenge studies. Numerous studies have been performed using experimental RSV infection in human participants. To date, in hVIVO's studies, over 1220 healthy participants (18 to 55 years of age) have been successfully and safely inoculated with RSV-A Memphis 37b. These studies demonstrated that adults could be infected by nasal inoculation and that experimental infection was safe. This strain has been shown to cause symptoms and virus shedding that closely match natural infection.

Administration of study intervention and challenge with RSV-A Memphis 37b will take place in hVIVO's specialised Clinical Units, either in the Quarantine Unit or Screening Clinic Units. Standard study procedures (including collection of blood, urine, and nasopharyngeal secretions for assessment of safety and efficacy) have been employed in previous studies conducted by hVIVO.

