#### 8.8. Electrocardiogram

Study specific normal ranges are provided in Appendix 4.

Twelve-lead ECGs will be obtained to evaluate the electrical activity of the heart. ECGs will be read on site by an appropriately qualified Investigator. Wherever possible the same Investigator will review subsequent ECGs from the same participant for the assessment of any change from baseline.

Any changes from baseline during the study will be assessed for their clinical significance. Clinically significant changes will be reported as AEs. The PI or delegate will assess non-clinically significant changes to determine whether they should be recorded.

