#### **Laboratory Values**

Deterioration in a laboratory value (compared to baseline) should only be reported as an AE if the deterioration fulfils the criteria for an AE. If deterioration in a laboratory result is associated with clinical signs and symptoms, the sign or symptom will be reported as an AE and the associated laboratory result will be considered as additional information.

The Investigator and/or SME will judge whether abnormal laboratory values are clinically significant or not clinically significant, and record this in the source document. This entry should be signed and dated by the relevant Investigator. Laboratory abnormalities detected at screening will be considered as part of the medical history and will not be reported as AEs

Challenge Virus associated laboratory abnormalities (e.g.: elevated ALT, AST or GGT; decreased neutrophils) may be recorded as AEs (at the discretion of the Investigator).

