## 5.2 Data handling conventions

### 5.2.1 Definitions

#### 5.2.1.1 Baseline

Baseline is defined as the last non-missing measurement before dosing. This will usually correspond to the measurement performed at Day-1 before first-dose, unless overruled after review of data at the DRM or otherwise stated in the appropriate endpoint section(s) below, whatever the reason for that assessment (e.g. if it is a repeat assessment, then it should be used as the baseline). However, in case of missing value at Day-1 the last available value recorded during previous visits will be used as baseline value.

If all pre-dose measurements are missing then baseline will be considered as missing, and no changes from baseline and no percentage reduction from baseline will be computed.

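### Protocol section 8 does not require baseline to precede the dose, in conflict with the SAP; by study day it selects a post-dose ECG in Part 2

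*Protocol*

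**What the plan says.** Protocol section 8 gives one general rule: "For all study assessments, the value obtained nearest to dosing will be used as the baseline measure for assessments, unless stated otherwise". The closing proviso does not help for ECG, vital signs or laboratory values. Protocol 8.6, 8.8 and Appendix 3 (10.3.6.2) all refer to baseline without redefining it, and 8.9 fixes only the height used for spirometry.

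SAP 5.2.1.1 gives a different rule: "Baseline is defined as the last non-missing measurement before dosing". If the dosing-day value is absent, "in case of missing value at Day-1 the last available value recorded during previous visits will be used as baseline value". If nothing was measured before the dose, no later value is substituted: "If all pre-dose measurements are missing then baseline will be considered as missing". A post-dose value therefore cannot become baseline under the SAP's definition. SAP section 8 declares added endpoints, revised viral-shedding definitions and a changed sequence of analysis, but not this.

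Sites are told to use baseline when judging safety findings. For the ECG, "Any changes from baseline during the study will be assessed for their clinical significance", and clinically significant changes become adverse events. For blood results the rule is: "Deterioration in a laboratory value (compared to baseline) should only be reported as an AE if the deterioration fulfils the criteria for an AE".

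**The concern.** The value nearest to dosing is not necessarily a value before dosing. If a post-dose value serves as baseline, any change that had already occurred by then counts as zero change at the site. The SAP would count the same change in full. The two documents would then measure the same participant against different references, one feeding the adverse event record and the other the safety tables.

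The trial's own safety definitions also need a pre-dose reference. SAP 4.2.2.1 defines a treatment-emergent event as one absent before the first dose. Protocol 10.3.1 excludes pre-existing conditions only if they were there before study drug or inoculation and do not worsen. Safety is a stated objective in both parts.

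**Working it through.** The plan gives no figure to reproduce. The check is to find which scheduled value each rule selects.

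**Inputs.** Part 2 dosing: "Study intervention I.V. dosing on Day -1" (Protocol 4.1.4). Admission assessments: "Can be performed on Study Day -3 or Study Day -2" (Protocol 1.3.2, note l; the marker on the ECG row is clearest in the SAP copy of the schedule). The Day -1 ECG is marked as taken after the dose (note o). Protocol 4.1.4 allows challenge 1 to 2 days after treatment. Part 1 vital signs are taken before and after the dose on Day 0 (Protocol 1.3.1, note d).

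**Part 2 ECG.** Distance from dosing in study days:
- admission ECG: Day -3 is |-3 - (-1)| = 2 days before; Day -2 is |-2 - (-1)| = 1 day before
- Day -1 post-dose ECG: 0 days

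The protocol rule selects the post-dose ECG and the SAP rule selects the admission ECG. By clock time, the post-dose ECG is nearest whenever its delay after dosing is shorter than the gap from the admission ECG to dosing. With delays of 0.25 to 12 hours and gaps of 24 or 48 hours, it was nearest in every case tried. The documents give no clock times. An exception would need a late Day -2 ECG together with a long-delayed post-dose ECG.

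**Part 1 vital signs.** Both readings fall on the dosing day, so either may be nearest. The SAP rule would always select the pre-dose reading.

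**Part 2 haematology and biochemistry.** Samples are drawn at admission and on Day 0 before challenge. In whole days from dosing:

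| Admission sample | Day 0 sample | Nearest |
|---|---|---|
| 2 days before (Day -3) | 1 day after | Day 0, post-dose |
| 2 days before (Day -3) | 2 days after | tie |
| 1 day before (Day -2) | 1 day after | tie |
| 1 day before (Day -2) | 2 days after | admission, pre-dose |

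Only one of the four combinations clearly selects a post-dose value. The documents do not say how participants will be distributed across them.

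**What the difference does.** SAP 5.6.4 tabulates QTcF and QTcB increases from baseline in bands at 30 and 60 ms. A rise seen on the Day -1 post-dose ECG enters that table as a change from the admission value. Under the protocol rule the same tracing is the reference, so its change is zero by construction.

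**The case against.** The strongest reply is that nobody would apply the sentence literally. The next paragraph of Protocol section 8 lets generic screening results serve as baseline, so the authors had pre-dose values in mind. The literal reading also gives an absurd result in Part 1. ECG, haematology, biochemistry and urinalysis are scheduled only at screening and on Day 12, so Day 12 is nearer to dosing for any screening on Day -28 to Day -13 (16 of the 28 permitted days). As evidence of intent this is fair. It does not settle the Part 2 ECG, where a post-dose tracing on the dosing day is a plausible candidate and nothing tells the site to pass over it.

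The second reply limits the consequence, and it stands. The SAP tables already use a pre-dose baseline. Adverse event capture does not depend on baseline alone: the definition in Protocol 10.3.1 is general, Appendix 4 gives absolute limits for vital signs and ECG intervals, and the C-reactive protein rule is absolute. ECGs are read by an investigator, where possible the same one each time, and the laboratory wording sets no numerical change threshold.

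Three stronger readings are tempting, and the documents support none of them.
- A reader might infer that an acute drug effect will be absorbed into baseline and adverse events lost. No acute ECG or laboratory effect is given. Protocol 4.3 reports no safety concern from earlier adult studies, and 2.3 names mild, transient dizziness and headache as the commonest side effect in adults.
- A reader might infer that everyone with Day -3 admission bloods takes a post-dose laboratory baseline. That holds only if challenge follows dosing by one day; at two days it is a tie.
- A reader might carry the argument to the 15% spirometry threshold in 10.3.6.2. If an acute fall *a* were captured as baseline, the total fall needed would be 1 - (1 - *a*) × 0.85, which is 19.25%, 23.5% or 27.75% for assumed values of 5%, 10% or 15%. These falls are assumptions, and the protocol does not say whether Day -1 spirometry precedes the dose.

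**Conclusion.** The two baseline definitions conflict, and the conflict is undeclared. The firm case is the Part 2 ECG. By study day, the protocol rule selects a post-dose tracing for all of the roughly 50 participants, provided the scheduled ECGs are done. Part 1 vital signs (about 6 participants) and one timing combination for Part 2 haematology and biochemistry are possible further cases.

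The effect on the SAP change-from-baseline tables and on efficacy is nil. The possible effect is confined to site judgement of change when raising adverse events, and to agreement between those records and the SAP tables. It cannot be quantified, because the documents give no acute effect, and absolute ranges and clinical judgement would contain part of it. This is a wrong reference rule that should be corrected; it is not evidence that events will be missed.

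**What to change.** Replace the baseline sentence in Protocol section 8 with the SAP rule: *baseline is the last non-missing value before dosing*. State the consequence for the Part 2 ECG explicitly: baseline is the admission ECG, or an earlier pre-dose ECG if that is missing, and the Day -1 post-dose ECG is the first on-treatment value.

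The cost is one or two protocol sentences. No assessment, sample size or SAP table changes. Declaring the difference in SAP section 8 would put it on record but would leave sites working to the other rule, so it is the weaker option.
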